7.2. Pharmacodynamic (PD) Assessment (s)

Not applicable.

7.3. Immunogenicity

Not applicable.

8. SAFETY EVALUATION AND REPORTING

8.1. Assessment of Safety Endpoint Event(s)

The safety endpoints include AEs, physical examination, vital signs, 12-lead ECGs, and clinical laboratory tests (standard hematology, serum chemistry including AST/ALT, coagulation, and urinalysis).

8.2. Adverse Event Collection and Reporting

All clinical AEs (see Section 8.4.1 for definitions) occurring after the subject signs the ICF and up to 30 d after the last dose of study drug (ie, Period 3 dosing), whether observed by the investigator or reported by the subject, will be recorded on the Adverse Event CRF page. Medical conditions (including clinical laboratory values/vital signs that are out of range) that were diagnosed or known to exist prior to Informed Consent will be recorded as part of medical history.

All AEs, serious adverse events (SAEs), are to be reported according to the procedures in Section 8.5.

All clinical laboratory results, vital signs, and ECG results or findings should be appraised by the investigator to determine their clinical significance. Isolated abnormal clinical laboratory results, vital sign findings, or ECG findings (ie, not part of a reported diagnosis) should be reported as AEs if they are symptomatic, lead to study drug discontinuation, dose reduction, require corrective treatment, or constitute an AE in the investigator's clinical judgment.

At each time point, the investigator will determine whether any AEs have occurred by evaluating the subject. Adverse events may be directly observed, reported spontaneously by the subject or by questioning the subject at each time point. Subjects should be questioned in a general way, without asking about the occurrence of any specific symptoms. The investigator must assess all AEs to determine seriousness, severity, and causality, in accordance with the definitions in Section 8.4. The investigator's assessment must be clearly documented in the study site's source documentation with the investigator's signature.

Always report the diagnosis as the AE or SAE term. When a diagnosis is unavailable, report the primary sign or symptom as the AE or SAE term with additional details included in the narrative until the diagnosis becomes available. If the signs and symptoms are distinct and do not suggest a common diagnosis, report them as individual entries of AE or SAE.

For events that are serious due to hospitalization, the reason for hospitalization must be reported as the SAE (diagnosis or symptom requiring hospitalization). A procedure is not an AE or SAE, but the reason for the procedure may be an AE or SAE. Pre-planned (prior to signing the ICF) procedures or treatments requiring hospitalization for pre-existing conditions that do not worsen in severity should not be reported as SAEs (see Section 8.4.2 for Definitions).

For deaths, the underlying or immediate cause of death should always be reported as an SAE.

Any serious, untoward event that may occur subsequent to the reporting period that the investigator assesses as related to study drug should also be reported and managed as an SAE.

The investigator should follow subjects with AEs until the event has resolved or the condition has stabilized. In case of unresolved AEs, including significant abnormal clinical laboratory values at the end of study assessment, these events will be followed until resolution or until they become clinically not relevant.

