The following procedures will be performed on Day 4 of each period:

- Blood samples for PK analysis at 72 and 84 h postdose
- Continuous monitoring of AEs and concurrent medication

6.4.6. Day 5

The following procedures will be performed on Day 5 of each period:

- Blood samples for PK analysis at 96 and 108 h postdose
- Continuous monitoring of AEs and concurrent medication

6.4.7. Day 6

The following procedures will be performed on Day 6 of each period:

- Blood samples for PK analysis at 120 and 132 h postdose
- Continuous monitoring of AEs and concurrent medication

6.4.8. Day 7

The following procedures will be performed on Day 7 of each period:

- Vital signs (blood pressure, heart rate, oral temperature and respiratory rate) at approximately 144 h postdose
- 12-lead ECGs at approximately 144 h postdose
- Blood sample for PK analysis at 144 h postdose
- Continuous monitoring of AEs and concurrent medication

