6.6. Check-out or Early Termination

The following procedures will be performed at check-out of Period 3 (Day 7) or upon Early Termination:

- Complete physical exam
- Body weight
- Vital signs (blood pressure, heart rate, oral temperature, and respiratory rate), if not already taken
- 12-lead ECGs, if not already taken
- Blood samples for:
 - Clinical laboratory tests (hematology and fasting serum chemistry); subjects will fast for approximately 10 h prior to check-out for the serum chemistry tests
 - Serum pregnancy test for all females
- Urine samples for clinical laboratory urinalysis tests
- Continuous monitoring of AEs and concurrent medication

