6.7. Follow-up

If a subject is withdrawn from the study due to an AE, the subject will be asked to complete, at a minimum, assessments of the early withdrawal visit. If the AE has still not resolved, additional follow-up will be conducted, as appropriate, based on the investigator's judgment, and documented in the subject's medical records. At a minimum, serious adverse events (SAEs) should be followed for 30 d after the subject's last dose of study drug.

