Table 16.3: Schedule of Events (Days 2 to Check of Period 3 or Early Termination)

Study Period →	Periods 1, 2, and 3 ^a												Check-out of Period 3 or Early Termination	
Study Day ^b →	2		3			4		5		6		7		
Study Event ↓ Study Hour →	24	28	32	36	48	54	60	72	84	96	108	120	132	144
Complete physical exam														X
Body weight														X
Serum pregnancy test														X
Hematology, serum chemistry, urinalysis														X
12-lead ECGs	X													X X ^c
Vitals (BP, HR, temp, RR)	X													X X ^c
PK blood collections	X	X	X	X	X	X	X	X	X	X	X	X	X	
AE monitoring	<----- X ----->													
Record of concomitant medication	<----- X ----->													
Confinement	<----- X ----->													

Abbreviations: AE = adverse event; BP = blood pressure; ECG = electrocardiogram; d = day; h = hour; HR = heart rate; PK = pharmacokinetic; RR = respiratory rate; temp = oral temperature

^a There will be at least a 6-d washout between the dose administered in Period 1 and that in Period 2, and the dose administered in Period 2 and that in Period 3. Periods 2 and 3 will start after the last PK sample of the previous dose from period 2 and 3, respectively.

^b Study days are representation of days in each period.

^c If not already taken.

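### Adverse events are to be recorded to 30 days after the Period 3 dose, but completers are last asked about them at check-out (144 h), which leaves 24 days without a scheduled question

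*Combined protocol and SAP*

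**What the plan says.** Section 8.2 sets the recording window: adverse events "occurring after the subject signs the ICF and up to 30 d after the last dose of study drug", with the last dose specified as the Period 3 dose. It also names the ways an event can come to light: "Adverse events may be directly observed, reported spontaneously by the subject or by questioning the subject at each time point".

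The scheduled time points end at check-out. Section 6.4.8 (Day 7, 144 h) lists "Continuous monitoring of AEs and concurrent medication", and Section 6.6 repeats it under a lead-in that fixes the timing: "The following procedures will be performed at check-out of Period 3 (Day 7) or upon Early Termination". The second schedule table, titled "Schedule of Events (Days 2 to Check of Period 3 or Early Termination", has check-out or early termination as its last column. The synopsis gives a study duration of about 21 days, from check-in to check-out.

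Three provisions reach beyond check-out:

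- Section 6.7 opens with subjects who leave because of an event: "If a subject is withdrawn from the study due to an AE, the subject will be asked to complete" the early-withdrawal assessments. It adds that "serious adverse events (SAEs) should be followed for 30 d" from the last dose.
- Section 8.2 covers events still open at the end: "In case of unresolved AEs, including significant abnormal clinical laboratory values at the end of study assessment", which are followed to resolution or until no longer clinically relevant. It also makes serious events judged related to study drug reportable after the window closes.
- Section 8.7 asks for notification of pregnancies up to 90 days after study drug is stopped.

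**The concern.** The plan chose a 30-day window but scheduled active ascertainment for only its first six days. Up to check-out, subjects are confined and monitored continuously. From then on, a completer with no open event has no planned contact, so two of the three capture routes in Section 8.2 (direct observation and questioning) stop together, leaving spontaneous report.

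Characterizing safety and tolerability is the only secondary objective (Section 2.1.2), and treatment-emergent events are tabulated by treatment, relationship and grade (Section 10.4.3.1). If nothing is recorded after check-out, the study report cannot tell a quiet month from a month in which nobody was asked. Events that were never reported cannot be recovered at analysis.

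**Working it through.** **Inputs**

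- End of recording window: 30 d after the Period 3 dose (Section 8.2).
- Last scheduled assessment for completers: 144 h after the Period 3 dose (Sections 6.4.8 and 6.6, Table 16.3; the synopsis has confinement to at least 144 h).
- Stated study duration: about 21 d (synopsis).
- Terminal half-life: 27 h (Section 1.2.1.4).
- Subjects: 24 randomized, at least 21 expected to complete (Section 10.5).

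**Step 1: reproduce the stated duration.** With three 7-day periods, the Period 3 dose falls on study Day 1 + 2 × 7 = 15 and check-out on Day 15 + 6 = 21, which matches the synopsis. With the minimum 6-day spacing between doses, the Period 3 dose falls on Day 1 + 2 × 6 = 13 and check-out on Day 19. In both cases check-out is 144 h after the last dose, so the stated duration ends there and includes no later contact.

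**Step 2: length of the gap.**

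- Window after the last dose: 30 × 24 = 720 h.
- Without a scheduled assessment: 720 − 144 = 576 h = 24 d.
- Share of the post-last-dose window: 576 / 720 = 80%.

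Because confinement lasts at least 144 h, a late check-out would shorten the gap slightly.

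**Step 3: does other text fill the gap?**

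| Provision | Who or what it covers | Finds new events in a completer with nothing open? |
|---|---|---|
| 6.7, first part | Subjects withdrawn because of an event | No |
| 6.7, 30-day rule | Serious events already known | No |
| 8.2, unresolved events | Events or laboratory abnormalities open at end of study | No, only incidentally |
| 8.2, after the window | Related serious events, once someone reports them | No scheduled contact |
| 8.7 | Pregnancy, on notification | No scheduled contact |

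None of these schedules a question to a completer between check-out and day 30.

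**Step 4: how much drug remains.** 144 / 27 = 5.33 half-lives; 0.5^5.33 = 0.025. About 2.5% of the drug remains at check-out by half-life. This bears on how much the gap matters, not on whether it exists.

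**The case against.** The strongest reply is that this is a preference rather than a defect. Spontaneous report is a capture route that Section 8.2 names in its own right, questioning is promised only at scheduled time points, and every such point has it. A recording window may properly be longer than the questioning window. That is correct, and no contradiction is claimed.

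A second reply is that 80% is a share of calendar days, not of risk. That also stands. Most of the drug is gone by check-out, and the first 144 h after each dose are spent under continuous monitoring. Section 1.4 describes single doses of 200 to 2400 mg in about 190 healthy subjects as generally well tolerated, against at most 400 mg per dose here. Section 8.3 places the hepatic events under continuous multiple dosing. These facts keep the point small.

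A third is that the windows could be aligned the other way, by ending routine collection of non-serious events at check-out. That would be consistent, but it gives up late non-serious events that the plan now sets out to record, and it departs from the 30 days that Section 6.7 uses for serious events. It is not an equivalent remedy.

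Finally, a call will not detect a symptomless rise in liver tests, and events a few weeks after discharge are harder to attribute. Both limits are real. Neither argues against asking once at the end of a window the protocol already sets.

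**Conclusion.** The concern holds as a low-severity point. For completers, 24 of the 30 days after the last dose have no scheduled adverse event assessment, and the visible text contains nothing that fills them. The likely effect is modest under-ascertainment of late events, mostly ones a subject would not volunteer. The documents give no rate of late or unreported events, so no number missed is claimed.

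The PK objectives are unaffected. No bias between treatments is expected: with the six sequences, each treatment comes last in two of them, assuming sequences are filled evenly.

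The conclusion assumes that material not visible here holds no follow-up contact: Figure 3.1 is not shown, the consent pages are removed and Table 16.2 appears incomplete. Sections 6.4 to 6.7 and Table 16.3 make a hidden contact unlikely, and a consent-form instruction to telephone the site would still be spontaneous reporting.

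**What to change.** Add one telephone contact at about 30 days after the last dose, with a sentence in Section 6.7 and a column in Table 16.3. The caller should ask in general, non-leading terms, as Section 8.2 already requires, about new adverse events and concomitant medication. Keep the 30-day window.

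Cost: 21 calls if only the expected minimum of completers is contacted, 24 if every randomized subject is. Each event found needs the usual investigator assessment and source record. The change needs a protocol amendment with IRB approval (Section 14.7), and the last contact moves to about 24 days after check-out. Since the plan already accepts events up to day 30, the safety data would not be complete before then in any case. No blood draws, clinic days or staff are added. The last scheduled liver tests would remain those at check-out.

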8.3. Adverse Events of Special Interest

Combined elevations of aminotransferases and bilirubin, either serious or nonserious and whether or not causally related, meeting the criteria of a potential Hy's Law case (total bilirubin level $\geq 2 \times$ ULN with simultaneously ALT or AST $\geq 3 \times$ ULN) should always be reported to the Sponsor as soon as possible following the procedures outlined in Section 8.5 for SAE reporting, with the investigator's assessment of seriousness, causality, and a detailed narrative.

Based on pooled data from 424 subjects who received pexidartinib, elevations of liver transaminases (up to Grade 3) and bilirubin have been observed in studies with pexidartinib, together with cases of drug-induced cholestasis. All these events occurred in subjects treated with pexidartinib in a continuous, multiple dose regimen. Cases of cholestasis have been observed in the first 8 wk, have generally resolved with treatment discontinuation, but in rare cases have been severe, requiring liver dialysis and had a protracted course (8 mo).

8.4. Adverse Event

8.4.1. Definition of Adverse Event

An AE is any untoward medical occurrence in a subject administered a pharmaceutical product and that does not necessarily have to have a causal relationship with this treatment. An AE can therefore be any unfavorable and unintended sign (including an abnormal clinical laboratory finding, for example), symptom, or disease temporally associated with the use of a medicinal product, whether or not considered related to the medicinal product (ICH E2A Guideline. Clinical Safety Data Management: Definitions and Standards for Expedited Reporting, Oct 1994).

It is the responsibility of investigators, based on their knowledge and experience, to determine those circumstances or abnormal clinical laboratory findings which should be considered AEs.

8.4.2. Serious Adverse Event

A SAE is any untoward medical occurrence that at any dose:

- Results in death,
- Is life-threatening,
- Requires inpatient hospitalization or prolongation of existing hospitalization,
- Results in persistent or significant disability/incapacity,
- Is a congenital anomaly/birth defect, or
- Is an important medical event.

Note: The term “life-threatening” in the definition of “serious” refers to an event in which the subject was at risk of death at the time of the event; it does not refer to an event which hypothetically might have caused death if it were more severe (ICH E2A Guideline. Clinical Safety Data Management: Definitions and Standards for Expedited Reporting, Oct 1994).

Medical and scientific judgment should be exercised in deciding whether expedited reporting is appropriate in other situations, such as important medical events that may not be immediately life-threatening or result in death or hospitalization but may jeopardize the subject or may require intervention to prevent one of the other outcomes listed in the definition above. Examples include allergic bronchospasm, convulsions, and blood dyscrasias or development of drug dependency or drug abuse.

Note:

- Procedures are not AEs or SAEs, but the reason for the procedure may be an AE or SAE.
- Pre-planned (prior to signing the ICF) procedures or treatments requiring hospitalizations for pre-existing conditions that do not worsen in severity are not SAEs.

8.4.3. Severity Assessment

The following definitions should be used to assess intensity of AEs (based on the National Cancer Institute (NCI) Common Terminology Criteria for Adverse Events [CTCAE], version 5.0):

- Grade 1: Mild; asymptomatic or mild symptoms; clinical or diagnostic observations only; intervention not indicated
- Grade 2: Moderate; minimal, local, or noninvasive intervention indicated; limiting age-appropriate instrumental activities of daily living (eg, preparing for meals, shopping for groceries or clothes, using the telephone, managing money)
- Grade 3: Severe or medically significant, but not immediately life-threatening; hospitalization or prolongation of hospitalization indicated; disabling; limiting
- self-care activities of daily living (ie, bathing, dressing and undressing, feeding self, using the toilet, taking medications, and not bedridden)
- Grade 4: Life-threatening consequences; urgent intervention indicated
- Grade 5: Death related to AE

8.4.4. Causality Assessment

The investigator should assess causal relationship between an AE and the study drug on the basis of his/her clinical judgment and the following definitions. The causality assessment must be made based on the available information and can be updated as new information becomes available.

- Related:
 - The AE follows a reasonable temporal sequence from study drug administration and cannot be reasonably explained by the subject's clinical state or other factors (eg, disease under study, concurrent diseases, and concomitant medications).

or
 - The AE follows a reasonable temporal sequence from study drug administration and is a known reaction to the drug under study or its chemical group or is predicted by known pharmacology.
- Unrelated:
 - The AE does not follow a reasonable sequence from study drug administration or can be reasonably explained by the subject's clinical state or other factors (eg, disease under study, concurrent diseases, and concomitant medications).

8.4.5. Action Taken Regarding Study Drug(s)

- Dose Not Changed: No change in study drug dosage was made.
- Drug Withdrawn: The study drug was permanently stopped.
- Not Applicable: Subject died, study treatment had been completed prior to reaction/event, or reaction/event occurred prior to start of treatment.

8.4.6. Other Action Taken for Event

- None
 - No treatment was required
- Medication required
 - Prescription and/or OTC medication was required to treat the AE
- Other

8.4.7. Adverse Event Outcome

- Recovered/Resolved
 - The subject fully recovered from the AE with no residual effect observed.
- Recovering/Resolving
 - The AE improved but has not fully resolved.
- Not Recovered/Not Resolved
 - The AE itself is still present and observable.
- Recovered/Resolved with Sequelae
 - The residual effects of the AE are still present and observable.

- Include sequelae/residual effects.
- Fatal
 - Fatal should be used when death is a direct outcome of the AE.
- Unknown

8.5. Serious Adverse Events Reporting—Procedure for Investigators

All AEs, SAEs will be reported in the CRF.

The following types of events should be reported by the investigator on a SAVER (Serious Adverse Event Report) form within 24 h of awareness:

- SAEs (see Section 8.4.2 for definition)

All AEs, AESIs, and SAEs will be reported in the eCRF.

SAEs and AESIs (Section 8.3) should be reported by the investigator on a Serious Adverse Event Report (SAVER) form within 24 h of awareness (see Section 8.4.2 for the definition of an SAE).

All events (serious and non-serious) must be reported with investigator's assessment of the event's seriousness, severity, and causality to the study drug. A detailed narrative summarizing the course of the event, including its evaluation, treatment, and outcome should be provided. Specific or estimated dates of event onset, treatment, and resolution should be included when available. Medical history, concomitant medications, and clinical laboratory data that are relevant to the event should also be summarized in the narrative. For fatal events, the narrative should state whether an autopsy was or will be performed and include the results if available. Source documents (including medical reports) will be retained at the site and should not be submitted to the Sponsor for SAE reporting purposes.

Urgent safety queries must be followed up and addressed promptly. Follow-up information and response to non-urgent safety queries should be combined for reporting to provide the most complete data possible within each follow-up.

All completed SAVER forms must be signed by the investigator and e-mailed to [contact]. See Section 14.10.5 for contact information for SAE reporting. Please call the local SAE Hotline or your study monitor for any questions on SAE reporting.

8.6. Notifying Regulatory Authorities, Investigators, and Institutional Review Board/Ethics Committee

DSI and/or Worldwide Clinical Trials Early Phase Services, LLC will inform investigators, Institutional Review Boards/Ethics Committees (IRBs/ECs), and regulatory authorities of any Suspected Unexpected Serious Adverse Reactions (SUSARs) occurring in other studies of the investigational drug, as appropriate per local reporting requirements. DSI and/or CRO will comply with any additional local safety reporting requirements.

In the US, upon receipt of the Sponsor's notification of SUSARs that occurred with the study drug, unless delegated to the Sponsor, it is the investigator's responsibility to inform the IRB per Sponsor's instruction.

8.7. Exposure in Utero During Clinical Studies

DSI must be notified of any subject who becomes pregnant while receiving or within 90 d of discontinuing the study drug.

DSI must be notified of any male subject whose female partner becomes pregnant while the subject is receiving or within 90 d of discontinuing the study drug. Reporting after Early Termination is done voluntarily by the investigator.

Although pregnancy is not technically an AE, all pregnancies must be followed to conclusion to determine their outcome. This information is important for both drug safety and public health concerns. It is the responsibility of the investigator, or designee, to report any pregnancy in a female subject using the Exposure In Utero (EIU) Reporting form. Please contact your study monitor to receive the EIU Reporting form upon learning of a pregnancy. The investigator should make every effort to follow the subject until completion of the pregnancy and complete the EIU Reporting form with complete pregnancy outcome information, including normal delivery and induced abortion. The adverse pregnancy outcome, either serious or non-serious, should be reported in accordance with study procedures. If the outcome of the pregnancy meets the criteria for immediate classification as a SAE (ie, post-partum complications, spontaneous or induced abortion, stillbirth, neonatal death, or congenital anomaly, including that in an aborted fetus), the investigator should follow the procedures for reporting SAEs outlined in Section 8.5.

For reports of pregnancy in the female partner of a male subject, the EIU form (or SAE form if associated with an adverse outcome) should be completed with the subject's randomization number, initials, and date of birth, and details regarding the female partner should be entered in the narrative section.

